1.1 Study design

This study will be a multisite, randomized, sham-comparator controlled clinical trial conducted by Gaylord Specialty Healthcare Physical Therapy, (GSHPT) in Wallingford, Cheshire, Cromwell, Madison, CT, and the University Of Connecticut Health Center (UCHC) in Farmington, CT. All physical therapy related sessions will be conducted at the GSHPT locations listed above. Due to the nature of the intervention, participants and investigators will not be able to be masked to the intervention.

Participants may not know they are in the intervention or sham group and therapists will not confirm or deny their placement. The assessor will not be able to be masked to group assignments, as the presence or absence of certain variables in the dataset, namely the use of BFR inflation, will immediately reveal group assignment.

Sample size:

An *a priori* power analysis for a two-tailed t-test was performed for sample size estimation. With an alpha = .05, power = 0.80, and effect size of 0.635, the projected sample size needed for complete data sets is approximately N = 80. Thus, our proposed sample size of N = 96 will be more than adequate for the main objective of this study, and should also allow for an expected attrition rate of 20%.

Recruitment for this study will remain open until the target N of 80 complete datasets have been collected. This power analysis was performed using data from Dolak's¹ study on PFPS conducted in 2011. Sample size and protocol was also influenced by Brightwell's study on BFR after patellar instability².

Study Timeline:

Participants will be enrolled in the study for approximately 1 year. Starting with their evaluation and consent at the beginning of their therapy sessions, they will complete prescribed therapy and continue to complete PROs within 4-week, 9-week, 6-month and 12-month intervals. We anticipate the study will take approximately 3 years to complete.

Participants and Settings:

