Consented subjects will be assigned to either the sham-comparator control group or BFR Intervention Group according to a pre-generated randomized assignment sheet. Each randomized assignment sheet will consist of equal control and equal BFR assignments whose order has been randomized using the random list generator at <https://www.random.org/lists/>. We will use blocked randomization to reduce the risk that patients will be assigned to the BFR treatment and sham control groups at unequal frequencies. These blocks will have a size of 6. Co-Investigators at each site will be given a unique list with a number of assignments that is in proportion to the number of subjects expected to be recruited at the site; additional assignment lists will be generated if needed. These co-Investigators will be responsible for communicating group assignments to study therapists delivering the intervention, and for ensuring that randomization and treatment order is maintained. It is expected that if the assignment scheme is not maintained for whatever reason, that they will report the incident to the PI and how it was/or still needs to be rectified. No matter group assignment, all consented subjects will be asked to conduct all assessments. Utilizing a proposed sample size of 96 participants, the study will continue until there are at least 40 participants who complete all study related activities in both the intervention and control groups.

Study protocol:

After being identified as a potential study participant and being consented, participants will be randomly assigned to the sham control or BFR group. All physical therapy sessions will consist of typical, standard

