1.2 Data collection and analysis

Along with their standard therapy session reassessments (including routine session notes and progress notes), participants will be asked to complete the PROs at 4-week, 9-week or at the end of PT sessions, 6-month and 12-month intervals. The PROs will be completed by paper and pen while at a therapy session. Baseline, 4-week, and 9-week or end of PT sessions assessments will be completed as part of the routine PT session evaluation process. If the participant is not coming in to Gaylord for appointments, the 6 and 12-month assessments will be completed by phone with the participant or paper copies will be mailed to their last known address. If necessary, an email will be sent to remind them of the study and scheduled assessments.

Information regarding the security of participant's data will be shared with them in the consent form as well as upon request. All information collected specifically for the study will be stored on password protected computers in locked offices. The paper copies of the assessment forms completed as part of routine PT sessions will be stored according to Gaylord procedures in the hard copy of the patient's medical record. Information from the forms will be pulled by study staff and shared across sites only after it is de-identified.

After data is collected and de-identified, it will be analyzed using GraphPad Prism version 9.3.1, or other appropriate statistical software as necessary. Adjustments for abnormal distribution and unequal variance will be applied as necessary. To compare pre- and post-intervention measurements over time on subjective and objective outcome measures, we will use a two-way repeated measures analysis of variance or independent samples t-test to determine the effect of treatment groups (BFR + standard of care therapy and sham + standard therapy). For relationships between variables, we will use correlation and regression analyses as necessary. For categorical data, we will use chi-square testing or Fischer's exact test as necessary. Exact analysis for each test will depend on variance and distribution/normality of data set. We will perform an interim analysis at 50 % participant recruitment in order to assess the effects of the BFR therapy and safety for the subjects, and potential for change in sample size. We will not preclude the possibility of conducting other post-hoc data analyses as appropriate and approved by the IRB.

References

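### The treatment-effect test is left as ANOVA or t-test, with no stated effect or score and no baseline covariate or site term; a pre-named ANCOVA closes the gap at almost no cost.

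*Combined protocol and SAP*

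**What the plan says.** Section 1.2 holds all the analysis text available for review. Its purpose is stated as "To compare pre- and post-intervention measurements over time on subjective and objective outcome measures", and the method is a "two-way repeated measures analysis of variance or independent samples t-test to determine the effect of treatment groups". It adds: "Exact analysis for each test will depend on variance and distribution/normality of data set". Regression is mentioned only for relationships between variables, not for the treatment effect. The section also says: "We will perform an interim analysis at 50 % participant recruitment in order to assess the effects of the BFR therapy". The same sentence gives safety and a possible change in sample size as further purposes. No alpha is given for this look.

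In section 1.1, under Sample size, a "power analysis for a two-tailed t-test was performed for sample size estimation". Its inputs are given as "With an alpha = .05, power = 0.80, and effect size of 0.635", leading to 80 complete data sets. These inputs are tied to no outcome, visit or type of score. The enrolled number is called "more than adequate for the main objective of this study", but the available text does not name that objective. The opening part of the document was not available and may name it.

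Under Subject assignment, "Co-Investigators at each site will be given a unique list", in blocks of 6. Four sites recruit. The patient-reported outcomes are collected at evaluation, 4 weeks, 9 weeks or end of therapy, 6 months and 12 months.

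**The concern.** The plan permits several different tests of the same question. A repeated measures ANOVA yields a group effect and a group-by-time interaction. A t-test can compare follow-up scores or changes. These can lead to different conclusions from the same data, and the plan does not say which one counts. The pre/post wording leans towards change or interaction without settling it. Naming a main objective in the opening part of the document would not settle it either, because test, effect and score would still be open.

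The plan also gives up precision. The ANOVA uses baseline as one level of time, but no option uses it as a covariate. Site governs the randomisation lists yet is absent from the analysis.

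Finally, an interim look at treatment effects with no stated alpha or role leaves the overall error rate undefined.

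**Working it through.** **Inputs.** From section 1.1: d = 0.635, two-sided alpha 0.05, 40 completers per arm, four sites. Assumed, because the documents do not give it: correlation r between baseline and follow-up of 0.3, 0.5 or 0.7, with equal SDs at the two times. The plan does not say which SD scales d, so both cases are shown.

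**The plan's own figure.** A two-sample t-test with 40 per arm has noncentrality 0.635 × √(40/2) = 2.84 on 78 df, giving power 0.801. The total of 80 reproduces.

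**Scale A: d on the follow-up SD.** The effective effect is d for the follow-up t-test, d/√(2(1−r)) for the change t-test and d/√(1−r²) for ANCOVA (77 df). At r = 0.5 the ANCOVA value is 0.635/√0.75 = 0.733.

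**Scale B: d on the change-score SD.** The effect in follow-up SD units becomes 0.635 × √(2(1−r)) = 0.751, 0.635 and 0.492 at r = 0.3, 0.5 and 0.7. The scale A formulas then apply to these values.

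| | r = 0.3 | r = 0.5 | r = 0.7 |
|---|---|---|---|
| A: follow-up t-test | 0.80 | 0.80 | 0.80 |
| A: change t-test | 0.66 | 0.80 | 0.95 |
| A: ANCOVA | 0.84 | 0.90 | 0.975 |
| A: the two t-tests disagree | 27% | 23% | 20% |
| B: follow-up t-test | 0.91 | 0.80 | 0.58 |
| B: change t-test | 0.80 | 0.80 | 0.80 |
| B: ANCOVA | 0.94 | 0.90 | 0.86 |
| B: the two t-tests disagree | 18% | 22% | 36% |

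Disagreement means that one test is significant at 0.05 and the other is not (60,000 simulated bivariate normal trials per cell). With no true effect, reporting the better of the two t-tests after seeing both gives an error rate of 0.087 to 0.094.

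**Cost of the covariates.** At r = 0, ANCOVA gains nothing over the follow-up t-test. Three site terms reduce the df from 77 to 74 and cost less than 0.001 in power (at r = 0.5, 0.8991 against 0.8994).

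**Five-visit ANOVA (scale A).** Equal correlations and the same d at each affected visit are assumed. The interaction has 4 and 312 df and noncentrality 20 × Σ(eₜ − ē)²/(1−r), where eₜ is the effect at visit t and ē its mean over the five visits. The group effect has effective size ē/√((1+4r)/5).

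| | r = 0.3 | r = 0.5 | r = 0.7 |
|---|---|---|---|
| Single-visit ANCOVA | 0.84 | 0.90 | 0.975 |
| Constant effect: interaction | 0.67 | 0.83 | 0.97 |
| Constant effect: group effect | 0.92 | 0.83 | 0.73 |
| Effect at 4 and 9 weeks only: interaction | 0.86 | 0.955 | 0.998 |

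For the early-only effect, the single-visit ANCOVA is the one at 9 weeks. The baseline-adjusted mean of all four follow-ups would then have only 0.62/0.63/0.75, so the choice of contrast matters within ANCOVA too. The group effect averages in the pre-treatment score, so over five visits it estimates 4/5 of a constant effect (2/3 over three visits).

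**Interim look.** If both looks were tested at 0.05 and both could claim efficacy, the test statistics would have correlation √t, where t is the information fraction. The overall error is 0.083 at t = 0.5 and 0.091 at t = 0.25. The lower fraction allows for outcome data lagging behind recruitment. A split of 0.001 and 0.049 gives 0.0492 and 0.0496.

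**The case against.** The strongest case against has four parts.

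- **The disagreement figures compare two t-tests, while the plan's stated choice is ANOVA or t-test.** With only two times, the interaction and the change t-test are the same test and cannot disagree, and the pre/post wording leans that way. This is fair as a limit on the figures. However, the text does not exclude a follow-up t-test, and the plan has up to five times, not two. The error of about 0.09 does presuppose running both tests and reporting the better one.
- **ANCOVA's advantage over the ANOVA is uneven.** This stands. Under a constant effect at r = 0.7 it is nil against the interaction, and for an early-only effect the interaction is more powerful. The power claim is therefore limited to t-tests at the same visit.
- **The size of the gain rests on r and the scale of d, neither of which is in the documents.** This also stands, and is why ranges are given. The gap in specification does not depend on either.
- **The interim error is conditional on an efficacy claim that the plan does not make, and splitting alpha does not deal with a sample size change made after seeing treatment effects.** Both are correct; the second needs its own rule.

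The sentence about distribution and normality can be read as covering only the usual choice between parametric and nonparametric tests. Even so, effect and score remain open. No power gain is claimed for the site term, since site variance is unknown; it makes the analysis match the randomisation.

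**Conclusion.** The concern holds, as something the sponsor should correct rather than a flaw that invalidates the trial. The available text does not identify the test on which the conclusion rests. For r from 0.3 to 0.7, two permitted t-tests on the same outcome and visit disagree in 18% to 36% of trials with a true effect of the planned size. ANCOVA at that visit is more powerful than either t-test on both scalings of d: by about 4 to 17 points over the follow-up t-test on scale A, and by about 6 to 14 points over the change t-test on scale B. Confidence is high on the missing specification; the size of the power gain depends on the assumed correlation.

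**What to change.** Before any outcome data are examined:

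1. Name one primary outcome and one primary time or contrast. The choice is the team's; if the opening part of the document already names the outcome, refer to it here.
2. Test it by ANCOVA, or by a mixed model with one named contrast, with arm, baseline score and site as terms.
3. Keep the t-test and the repeated measures ANOVA as sensitivity analyses, stating which score or effect is read.
4. State whether 0.635 is on the follow-up SD or the change-score SD.
5. State whether the interim look can support an efficacy claim. If it can, give it its own small alpha, for example 0.001 with 0.049 at the end. If not, say so. Set out separately how any sample size change would be decided.

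The cost is SAP wording and slightly more analysis work, with no new data, visits or participants. Section 1.2 already allows other software. Testing at 0.049 rather than 0.05 costs about 0.002 in power (0.897 against 0.899 at r = 0.5 with site terms). The drawbacks are less freedom to choose the test later, no gain over the follow-up t-test if r is near 0, and less power than the interaction test if the effect is confined to the early visits.
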